10.4 Labeling

Bottles of investigational products will be labeled by Murty Pharmaceuticals to include the following required statement – Caution: New Drug – limited by federal law to investigational use. Bottles will be distributed to investigational sites. The following information will be completed when a subject is assigned to a study group: subject's study identification number and site code. In addition, stickers will be provided with the words "Study Week X", where X is the study week number (i.e., 1 through 12), and date dispensed.

The label will also include a warning indicating that the investigational product should be kept out of children's reach. Special emergency wallet cards will be prepared for each site indicating the local Principal Investigator's name and 24-hour emergency telephone number. The study subject should be instructed to carry these cards with them at all times.

10.5 Storage

Investigational products will be stored at room temperature without exposure to direct sunlight in a secure location in the distributing pharmacy or at each investigator's facility.

10.6 Record of Administration

Accurate recording of all investigational product dispensing/administration will be made in the appropriate section of the CRF. On the first clinic visit of each week, subjects will be asked to return the bottle and all unused investigational product. Unused investigational product will be inventoried for discrepancies. Subjects who have not been taking their tablets regularly will be encouraged to do so in the future. New, unused investigational products (a 10-day supply) will then be dispensed to that subject. On each and all clinic visits (i.e. 3 times per week), self-reports of investigational product use since the last clinic visit will be recorded.

10.7 Used/Unused Investigational Products

During the study, all investigational products not used by the subject must be returned to the investigator for assessment of subject compliance. At the end of the study, all unused investigational products must be inventoried. If any investigational product is lost or damaged, its disposition should be documented. Unused investigational products will be returned to Murty Pharmaceuticals when indicated by NIDA or KAI and retained at Murty Pharmaceuticals until the end of the study.

11 INTERVENTIONS

11.1 Investigational Products

Subjects assigned to receive bupropion hydrochloride SR will receive 150 mg every day for the first 3 days of dosing which will be increased to 300 mg daily (one tablet twice a day) for the duration of dosing period until the final dose taper. The dose will be tapered to 150 mg every day for 3 days until termination or the last scheduled day of the 12-week intervention period. Subjects will be informed that they must taper the dose for three days before stopping the investigational products completely in the event that they decide to terminate from the study prematurely. Subjects assigned to the placebo group will receive matched placebo on the same schedule as the bupropion group. Subjects will be instructed to take investigational products at least 8 hours apart when taking investigational products twice daily and not to take two tablets at once if a dose is missed. During the last 3 days of study interventions during Week 12 or before termination, subjects' investigational products will be tapered down to 150 mg (or equivalent placebo) each day by taking only one tablet per day.

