Risk of Seizure. Predisposing factors that may increase the risk of seizure with bupropion use include history of head trauma or prior seizure, central nervous system (CNS) tumor, the presence of severe hepatic cirrhosis, and concomitant medications that lower seizure threshold. Circumstances associated with an increased seizure risk include, among others, excessive use of alcohol or sedatives (including benzodiazepines); addiction to opiates, cocaine, or stimulants; use of over-the-counter stimulants and anorectics; and diabetes treated with oral hypoglycemics or insulin. Concomitant medications such as antipsychotics, antidepressants, theophylline, and systemic steroids are known to lower seizure threshold. The risk of seizure may be minimized if

the total daily dose of bupropion SR dose not exceed 300 mg, which is the dose planned in this study.

In addition, bupropion SR should be administered with extreme caution to subjects with a history of seizure, cranial trauma, or other predisposition(s) toward seizure, or patients treated with other agents (e.g., antipsychotics, antidepressants, theophylline, systemic steroids, etc.) that lower seizure threshold. These subjects will be excluded from participation in the study; moreover, these medications are prohibited during the intervention phase of the study.

Allergic Reactions. Anaphylactoid/anaphylactic reactions characterized by symptoms such as pruritus, urticaria, angioedema, and dyspnea requiring medical treatment have been reported at a rate of about 1 to 3 per thousand in clinical trials of bupropion SR. In addition, there have been rare spontaneous postmarketing reports of erythema multiforme, Stevens-Johnson syndrome, and anaphylactic shock associated with bupropion. Subjects will be advised to stop taking investigational products and consult a doctor if experiencing allergic or anaphylactoid/ anaphylactic reactions (e.g., skin rash, pruritus, hives, chest pain, edema, and shortness of breath) during treatment. Arthralgia, myalgia, and fever with rash and other symptoms suggestive of delayed hypersensitivity have been reported in association with bupropion. These symptoms may resemble serum sickness.

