12.12 Study Termination

12.12.1 Subject Termination

An investigator may terminate a subject if s/he deems it clinically appropriate or for any of the following reasons: (1) significant side effects from investigational products, (2) serious or unexpected AEs, (3) failure to comply with the study protocol, (4) protocol violation, (5) positive pregnancy test, (6) serious intercurrent illness or a benzodiazepine or barbiturate medication use (see below), and (7) the subject becomes a danger to self or others. Persistent alcohol abuse will be assessed by the PI or study physician and after the third warning and consultation with NIDA, the subject may be terminated from the study.

Benzodiazepine and Barbiturate Abuse. If a subject is found to be persistently abusing a benzodiazepine or barbiturate medication while in the study, they will likewise be given a warning by the site principal investigator or study physician to stop using these drugs, and continued abuse of a benzodiazepine or barbiturate beyond 3 weeks after the date the warning was given may result in discontinuation of bupropion. A three-week interval is warranted due to the long elimination time of some benzodiazepines. If a subject is prescribed a benzodiazepine or barbiturate for legitimate medical purposes, subjects will be warned that any abrupt discontinuation of either medication is known to lower seizure threshold.

Failure to comply with protocol. A subject will no longer be eligible for study participation, if s/he is absent from the clinic for more than two consecutive weeks and does not provide any data. A subject's study participation will end if s/he fails to provide six consecutive urine samples. In any event, subjects will be contacted 4 weeks after completing study interventions to schedule a follow-up interview.

Voluntary withdrawal. A subject may withdraw from the study anytime s/he wishes. In the event a subject is discontinued from receiving the investigational products, s/he will be allowed to continue the CBT with the approval of the site principal investigator.

Any subject, who discontinues prematurely, regardless of the reason, will be requested to return for a final visit to perform the necessary procedures and obtain data for the final assessments to be completed at the end of the study intervention phase as well as 4 weeks later for the follow-up interview.

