14.7 Serious Adverse Events

Each adverse event or reaction will be classified by the study investigator as serious or nonserious. Based on the seriousness of the adverse event or reaction appropriate reporting procedures will be followed. The International Conference on Harmonization (ICH) Guideline for Industry: Clinical Safety Data Management: Definitions and Standards for Expedited Reporting, ICH-E2A March 1995, as implemented by the U.S. Food and Drug Administration defines serious adverse event (SAE) or reaction as any untoward medical occurrence that at any dose:

- results in death;
- is life-threatening; (NOTE: The term "life-threatening" in the definition of "serious" refers to an event in which the patient was at risk of death at the time of the event; it does not refer to an event which hypothetically might have caused death if it were more severe.)
- requires inpatient hospitalization or prolongation of existing hospitalization;
- results in persistent or significant disability/incapacity; or
- is a congenital anomaly/birth defect.

In addition, important medical events that may not result in death, be life-threatening, or require hospitalization may be considered a serious adverse drug reaction, when based on appropriate medical judgment that may jeopardize the subject and may require medical or surgical intervention to prevent one of the outcomes listed in the above definition. Subjects that become pregnant during study participation will be taken off study drug. However, subjects may continue to receive counseling for substance abuse or be referred for appropriate treatment. Subjects will be asked to sign a release of information form for study personnel to access medical records to obtain information regarding the outcome of the pregnancy.

An unexpected event is one that is not described with respect to nature, severity, or frequency in the current Investigator's Brochure or product package insert.

Reporting of AEs and SAEs is described in **Appendix I.** There can be serious consequences including ultimately, criminal and/or civil penalties for Sponsors who fail to comply with FDA regulations governing the reporting of SAEs to FDA. The study investigators in this study have the responsibility of promptly reporting all SAEs to NIDA in order that the NIDA, as the IND Sponsor, can comply with these regulations.

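### The three-day taper before termination (11.1) has no exception by reason and is not reconciled with the instructions to stop product at an allergic reaction (4.2.5) or to discontinue a subject endangered by it (12.9)

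*Protocol*

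**What the plan says.** Section 11.1 has three taper sentences.

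- General: "The dose will be tapered to 150 mg every day for 3 days until termination or the last scheduled day of the 12-week intervention period".
- Conditional, addressed to subjects: "they must taper the dose for three days before stopping the investigational products completely", and this applies "in the event that they decide to terminate from the study prematurely".
- General: "During the last 3 days of study interventions during Week 12 or before termination, subjects' investigational products will be tapered down" to one tablet a day.

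The synopsis mentions only the scheduled taper at the end of the 12 weeks and is silent on early termination.

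The provisions for stopping are elsewhere.

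- Section 4.2.5, Allergic Reactions: "Subjects will be advised to stop taking investigational products and consult a doctor if experiencing allergic" or anaphylactic symptoms, with examples such as rash, hives and shortness of breath. No taper is mentioned.
- Section 12.9: a subject whom the site principal investigator or study physician judges to be in grave danger because product use is continuing is discontinued from the study and connected with a treatment agency. No taper is mentioned.
- Section 14.7: "Subjects that become pregnant during study participation will be taken off study drug". No timing is given.
- Section 12.12.1: an investigator may terminate a subject for reasons that include "1) significant side effects from investigational products, (2) serious or unexpected AEs" and a positive pregnancy test. It does not say when dosing ends.

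**The concern.** Termination is the protocol's own term, and section 12.12.1 includes safety reasons under it. Neither general taper sentence in 11.1 excludes those reasons. Read literally, they put three more days of product before a termination that follows an event for which another section says stop.

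The conditional sentence can collide as well. A subject who develops hives and decides to leave the study has been told to stop (4.2.5) and told to taper first (11.1). Both instructions are addressed to the subject, and section 10.3 provides a 10-day supply at a time, so tablets for a taper may well be at home.

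At stake is whether a site or a subject can tell from the protocol what to do on the day of the event. A secondary matter is causality assessment: Appendix I, section C, lists what happened after the drug was discontinued among the considerations for relatedness, and an abrupt stop and a taper give different evidence there.

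**Working it through.** The protocol gives no statistic to reproduce. The check sets the passages side by side, case by case.

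1. **Allergic or anaphylactoid reaction, participation ends.** 4.2.5 says stop. In 11.1, "During the last 3 days of study interventions during Week 12 or before termination" applies to any termination, and the conditional sentence also applies if the subject chose to leave. The instructions differ and nothing ranks them: a conflict.
2. **Allergic reaction, subject stops product but stays in the study.** Section 12.6 allows a subject to stop product while continuing therapy and assessments. There is no termination, so the 11.1 sentences tied to termination do not apply. No conflict.
3. **Grave danger from continued product use (12.9).** Here the subject is discontinued from the study, so the general sentences in 11.1 reach the case. The ground for discontinuation is continued use, while 11.1 puts three days of use before termination. A conflict, although 12.9 does not itself state the timing of the last dose.
4. **Pregnancy (14.7 and 12.12.1).** Coming off study drug could mean at once or after a taper. The two texts can be read together: an ambiguity.
5. **Other adverse-event terminations (12.12.1).** The provision is discretionary and silent on when dosing ends. It shows how far the unqualified taper wording reaches but does not contradict it: an ambiguity.

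**Size per subject.** From 11.1, 3 days × 150 mg per day = 450 mg between the two readings (matching placebo in the control group).

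**Order of magnitude for the number of subjects.** This is illustrative only, applying the rates in 4.2.5, which come from other trials, to the planned 100 bupropion subjects.

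- Anaphylactoid or anaphylactic reactions, about 1 to 3 per thousand: 100 × 0.001 = 0.1 to 100 × 0.003 = 0.3 expected.
- Discontinuation for skin disorders, 2.4%: 100 × 0.024 = 2.4 subjects.

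Neither figure counts subjects who would meet conflicting instructions. The second counts discontinuations for all skin disorders, whether or not an allergic reaction was involved. The protocol gives no rate for pregnancy, grave-danger or serious-event terminations.

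**The case against.** The strongest reply is that 4.2.5 is a specific instruction for a named event, and a specific rule ordinarily prevails over a general schedule. Stopping product is also separate from leaving the study: sections 12.6 and 12.12.1 both provide for subjects who stop product and continue therapy, and 14.7 lets a pregnant subject continue counseling. This narrows the conflict to cases where product and participation end together. It does not remove it. Section 4.2.5 is background safety text, 11.1 is the dosing section, and no precedence is stated.

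A reader might infer more than the documents support, in four ways.

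- *That the sentence telling subjects they must taper conflicts by itself with every stop for safety.* It covers only a subject's own decision to leave. The unqualified wording is in the other two sentences.
- *That the protocol directs sites to keep dosing after a reaction or a positive pregnancy test.* That is one possible reading. 4.2.5 says the opposite for allergy, and 14.7 is silent on timing.
- *That exposure and last-dose data will not be comparable across subjects or sites.* Product use is self-reported at every visit (10.6), tablets taken are reconstructed by timeline followback (13.6.23), and pills are counted weekly (Table 1, note j). Appendix I, section E, asks for the last dose before a serious or unexpected event and any action taken with the drug. What remains is a possible gap for a subject who leaves abruptly and does not return.
- *That sites will resolve the conflict differently.* The protocol refers to an Operations Manual (section 16) that is not shown and may give direction. Even so, the protocol's own text would still need to agree with itself.

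**Conclusion.** The point holds in a limited form. Section 11.1 requires a taper before termination without exception, 4.2.5 and 12.9 call for stopping or discontinuation on safety grounds, and nothing says which governs when both apply. For pregnancy and other adverse-event terminations the protocol is unclear rather than self-contradictory.

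The size is up to 450 mg over three days for an affected subject, and probably few subjects. This rests on reading termination in 11.1 in the sense used in 12.12.1, and on 11.1 containing no unstated exception. No efficacy estimate, error rate or sample size depends on it. It merits correction because it is a collision between stated rules on a safety matter and a short wording change repairs it.

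**What to change.** The sponsor and medical monitor should reconcile section 11.1 with 4.2.5, 12.9, 12.12.1 and 14.7. Section 11.1 should state which kinds of early stopping its taper sentences govern and which they do not, covering at least: the subject's own decision to leave, allergic reaction, danger from continued product use, other adverse-event termination, and pregnancy. The same scope should go into the instructions given to subjects. Which rule applies to each reason is a clinical decision for them, and none is proposed here.

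The cost is a few sentences in 11.1, matching subject instructions, and the IRB submission that section 14.2 requires for an amendment. Sample size, visit schedule and analysis are unaffected. Adding the last-dose date and whether a taper was taken to the End of Trial form is optional, since dosing is already recorded.

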11.2 Cognitive Behavioral Therapy

All subjects will be offered and encouraged to attend two 60 minutes early recovery skills group sessions per week after signing consent but before randomization. After randomization, the CBT program will consist of thrice weekly, 90-minute group sessions through the 12-week investigational product dosing period of the trial with once weekly sessions during the 4-weeks of follow-up. In order to help potential participants to stop methamphetamine use, they will be introduced to the counselors and scheduled to attend two 60-minute early recovery skills groups each week after signing informed consent up until randomization. Topics covered in this early recovery skills group include: Getting Rid of Paraphernalia; Triggers; Introduction to 12-Step Groups; and Brief Information on HIV. Concepts presented in these sessions include the following: (1) self-monitoring and relapse analysis; (2) identification of "triggers" and cognitive

strategies for coping with them; (3) teaching of problem solving skills; (4) education about methamphetamine and methamphetamine dependence; (5) education about HIV and reducing the risk of HIV transmission; and, (6) promotion of prosocial activities. The content of these group topics is prearranged and sequenced using a manualized format. This is a feasible treatment that is known to be well accepted by subjects and it represents an appropriate, ethically defensible standard treatment condition to serve as the "platform" for the medication trial. Staff members who provide CBT counseling will have attended training in the use of these materials. The CBT specialist will have a minimum of a master's degree (or equivalent). To ensure that the integrity of these sessions is maintained, some of the sessions may be audiotaped. Refer to the Operations Manual for further instructions on the quality assurance process. Our experience is that these sessions are valued by subjects and attendance is excellent. Thus, psychosocial involvement is seen as a standard or platform for the proposed pharmacotherapy evaluation.

12 STUDY PROCEDURES

12.1 Subject Recruitment

Interested subjects who are seeking treatment and are available to come to the clinic for 18-to-24 weeks will meet with the investigator or designated investigational staff and receive an explanation of the study purpose and requirements. If still interested after receiving an explanation of the study, the subject will be given an opportunity to review, inquire about, and sign the informed consent form. A separate consent form will be used for the genetics analysis part of the study. Recruitment strategies vary across each site based on their local population, however standard tactics will be used (i.e., flyers, newspaper ads, radio ads). Local IRBs and NIDA will approve all advertising materials used for subject recruitment. Once the subject signs the consent form, s/he will be considered enrolled in the study.

12.2 Screening/Baseline Assessments

Screening and baseline assessments will be conducted as shown in **Table 1**. Screening and baseline assessments may be performed concurrently. A single blood draw for genetic samples will be performed during the screening period for those subjects who consented to the genetics part of the study. This one draw will result in the collection of one tube of blood for genomic DNA analysis and two tubes of blood for RNA analysis. Two additional tubes of blood will be collected for baseline plasma bupropion and BDNF levels determination during screening. The blood for genomic DNA analysis will also provide data to be used in conjunction with genetic analysis of methamphetamine dependence, even if the subject is ultimately found ineligible to participate in the main study. Data that will be used in the genomic analyses include: demographic data, medical and substance use history (timeline followback, quantity frequency interview, methamphetamine urine levels), family history, and diagnostic information obtained by the MINI. Detailed information about what data will be used in the genetic part of the study is enumerated in a separate Genetics Informed Consent Form.

Screening/baseline assessments will occur over a consecutive 14-28 day period. A potential subject must complete the minimum set of baseline measures over a consecutive 14-day period to be eligible for the study. If a subject fails to satisfy eligibility criteria during the screening and baseline periods, s/he may be re-screened. This decision will be made on a case-by-case basis.

Baseline measures over the consecutive 14-day period include collection of at least four urine specimens prior to randomization and the accompanying other baseline repeated measures. Demographic data and the reason that any subject did not meet eligibility criteria must be recorded for anyone who consented to screening even if the individual is a screening failure.

